5.5.4. Patient Characteristics

For baseline patient characteristics summary, treatment groups are based on

[Group 1] EM120, EM240, CM120, CM240

[Group 2] LY120/LY120, LY240/LY240, PLA/LY120, PLA/LY240

[Group 3] EM_ALL, CM_ALL, LY_ALL

Hence, each summary will be created for these three groups.

If statistical comparisons are conducted, then following arm will be compared:

Group1: EM120 vs EM240, CM120 vs CM240.

Group2: None.

Group3: EM_ALL vs CM_ALL

Note that source of patient characteristics at baseline for EM patients are defined in the CGAP Protocol Section 2, Schedule of Activities, unless otherwise specified. For example, height is from CGAN Visit 3, and age is from CGAP Visit 3.

The following patient characteristics at baseline will be summarized

- Demographic (age, gender, race and subrace, height, weight, body mass index, Age [<20 , ≥ 20])

Note: body weight (as well as BMI) is based on the last observation before Visit 3 injection.

- Baseline MHD category per 30 day (<8, >=8) (EM: CGAN Month 6. CM: Visit 2 to Visit 3)
- Years since migraine diagnosis (EM: CGAP Visti3. CM: Visit 3)
- Migraine and headache related measures (EM: CGAN Month 6. CM: Visit 2 to Visit 3).
 - number of migraine headache days
 - number of migraine headache days with abortive (acute) medication use
 - number of migraine headache days or headache days with abortive (acute) medication use
 - number of headache days
- PGI-S (EM: CGAN Month 6. CM: Visit 3)
- MIDAS (total, each question) (EM: CGAN Month 6. CM: Visit 3)
- MSQ (total, 3 subscores) (EM: CGAN Month 6. CM: Visit 3)
- Previous migraine prevention treatment (Yes, No, Yes and did not fail, Yes and fail >=1, Yes and fail >=2) (EM: CGAN Visit 1, CM: Visit 1)
- Number of previous migraine prevention treatment fail (EM: CGAN Visit 1, CM: Visit 1)
- Past usage (yes/no) or current usage (yes/no) of followings: Alcohol, caffeine, nicotine replacement therapy, and tobacco and nicotine combined. (EM: CGAN Visit 1, CM: Visit 1)

Note: Except caffeine, summaries are based on patients with ≥ 20 years old.

- Medical history except primary medical conditions (at ICF). Medical history is defined as illness (es) that ended prior to the signing of informed consent (EM: CGAP Visit 3, CM: Visit 1). It will be summarized by preferred term (PT).
- Pre-existing condition (at ICF). Pre-existing conditions are those AEs existing at the study entry. It will be summarized by preferred term (PT) (EM: CGAP Visit 3, CM: Visit 1)

- Number of Comorbid conditions other than migraine. Comorbid conditions other than migraine are those AEs existing before Visit 3 and continuing after Visit 3 other than migraine. (i.e., not contained “migraine” as PT). If it ends on Visit 3, then it is not a comorbid condition. The count is based on PT. (2 events with different LLT but the same PT will be counted as one comorbid condition.) (EM: CGAP Visit 3, CM: Visit 3)

Comparisons between treatment groups will be performed using Fisher’s exact test for categorical data and ANOVA with treatment as independent variables in the model for continuous data.

Listing of Subjects Demographic will be created.

5.5.5. Exposure to Investigational Product

For exposure summary, treatment group is based on (EM120, EM240, CM120, CM240)

Patients will receive the investigational medicinal product (IMP) at the following planned time points:

- Beginning of Month 1 (Visit 3)
- Beginning of Month 2 (Visit 5)
- Beginning of Month 3 (Visit 6)
- Beginning of Month 4 (Visit 7)
- Beginning of Month 5 (Visit 8)
- Beginning of Month 6 (Visit 9)
- Beginning of Month 7 (Visit 10)
- Beginning of Month 8 (Visit 11)
- Beginning of Month 9 (Visit 12)
- Beginning of Month 10 (Visit 13)
- Beginning of Month 11 (Visit 14)
- Beginning of Month 12 (Visit 15)

The following will be derived from the information recorded on the eCRF:

- For treatment phase (Study Period III), duration of exposure in days is calculated as: treatment phase last visit date – first date IMP administered + 1.
- For treatment phase (Study Period III), number and percentage of patients with 1, 2, continuing up to 12 doses injected.

Comparisons between treatments for duration of IMP exposure will be performed using an ANOVA with treatment in the model.

Number of patients with 1 dose, 2, 3, ..., 12 doses injected will be compared between treatment groups with the Fisher's exact test.

Listing of Subjects with Exposure to Investigational Product will be created.

Listing of treatment exposure with Randomization Scheme and Codes will be created.

5.5.6. Treatment Compliance

For treatment compliance summary, treatment group is based on (EM120, EM240, CM120, CM240)

Treatment compliance will be calculated for Study Period III as:

$$\frac{\text{number of completed scheduled dosing visits in which the patient received planned injections} * 100}{\text{number of completed scheduled dosing visits, including any skipped dosing visits before the last dosing visit (Visit 15, inclusive) or early discontinuation visit (exclusive)}}$$

Comparisons between treatments for treatment compliance will be performed using an ANOVA with treatment in the model. For this analysis, a partial dose (for example, a patient only got one injection instead of two) will be considered as no dose received.

5.5.7. Patient Reported Outcomes Diary Compliance

For diary compliance summary, treatment group is based on (EM120, EM240, CM120, CM240)

Electronic patient reported outcomes diary compliance at each one month period and for overall will be calculated:

- SP III: baseline, Month 1, ..., Month 12, overall (Month 1 through Month 12) for ITT population
- SP IV: Month 13, ..., Month 16, overall (Month 13 through Month 16) for post treatment population

Diary compliance at each 1-month period (including baseline, Month 1, 2, 3, up to Month 16) as well as for Study Period III overall (Month 1 through Month 12) will be calculated. Diary compliance at each period is calculated as:

$$\frac{\text{Actual number of diary days in the period}}{\text{Expected number of diary days in the period}} \times 100$$

“Expected number of diary days in the period” is based on actual visit date for that particular period (Month)

Example: Expected number of diary days in the period Month 3 = date of Visit 7 – date of Visit 6 (diary for Visit 6, diary for Visit 6+1 day, ..., diary for Visit 7-1 day.)

For each patient, overall diary compliance for SP III is average of monthly compliance in SP III (Month 1,..., Month 12). If he discontinues early, then ignore the rest of the month. In this case, the last month compliance is based on max (30, the total number of calendar days in that month) (See Section 5.4.1).

Expected number of Diary days for Month 13, Month 14, Month 15, and Month 16 in SP IV is 30 days. Note that 2-month visit interval (e.g. Month 13 and Month 14) will be split into two one-month interval as defined in Section 5.4.1. The section explains how to handle early discontinuation case.

For each patient, overall diary compliance for SP IV is average of monthly compliance in SP IV (Month 13,..., Month 16). If he discontinues early, then ignore the rest of the month. In this case, the last month compliance is based on 30 days as the denominator (See Section 5.4.1)

In addition following will be summarized for each month and for overall:

- subjects with $\geq 80\%$ compliance
- subjects with $\geq 50\%$ compliance

Treatment comparisons for diary compliance for each month and for overall will be performed separately using an ANOVA with treatment in the model.

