Interval allowance (days) compared from previous visit				±3	±3	±7	±7	±7	±7	±7	±7	±7	±7	±7	±7	±7	±7	±7
Visit	1	2	3ª	4	5	6	7	8	9	10	11	12	13	14	15	16/ ET	17	18/ ET
Month			0	(D14)	1	2	3	4	5	6	7	8	9	10	11	12	14	16
Concomitant medications	X	X	X	X	X	X	X	X	X	X	X	X	X	X	X	X	X	X
Assessment of migraine and headache days ^e		X	X		X	X	X	X	X	X	X	X	X	X	X	X	X	X
Paper-diary training to patients		X																
Clinical Laborato	ry Tests ar	nd Sampling	Sche	dules								ı	ı	ı	ı			1
Hematology	X		X				X			X			X			X		X
Clinical chemistry	X		X				X			X			X			X		X
HbA1c			X							X						X		X
Urinalysis ^f	X		X							X						X		X
Serum Pregnancy (for women of childbearing potential) ^g or FSH at Visit 1 (for women who have evidence of cessation of menses for at least 12 months)	X															X		X
Urine pregnancy ^g			X		X	X	X	X	X	X	X	X	X	X	X			
Urine Drug Screening	X																	
Immunogenicity ^h			X	X	X	X	X			X			X			X		X

Study Period (SP)	SP I- Screening	SP II- Prospective Baseline	SP									SP IV – Follow- up						
(Target) Interval (days) since previous visit			30- 45	14	16	30	30	30	30	30	30	30	30	30	30	30	60	60
Allowable range (days) between visits	3-45	30-40a																
Interval allowance (days) compared from previous visit				±3	±3	±7	±7	±7	±7	±7	±7	±7	±7	±7	±7	±7	±7	±7
Visit	1	2	3ª	4	5	6	7	8	9	10	11	12	13	14	15	16/ ET	17	18/ ET
Month			0	(D14)	1	2	3	4	5	6	7	8	9	10	11	12	14	16
Biomarker storage sample ^h			X		X		X			X			X			X		X
CCI		X	X	X	X	X	X			X			X			X		X
PK blood sample h			X	X	X	X	X			X			X			X		X
CCI		X																
Whole blood RNA/epigenetic sample h			X							X						X		X
Study drug administered			X		X	X	X	X	X	X	X	X	X	X	X			
Scales, Questionn	aires, and	Outcome Me	asur	es	1		1							ı		1		
MIDAS			X				X			X			X			X		X
MSQ (v2.1)			X		X	X	X	X	X	X			X			X	X	X
HCRU and Employment Status			X		X	X	X	X	X	X	X	X	X	X	X	X	X	X
PSMQ-M					X					X						X		X
PGI-S			X		X	X	X	X	X	X						X		X
PGI-I					X	X	X	X	X	X			X			X		X
C-SSRS/ SHSF, SHFU ^j	X	X	X		X	X	X	X	X	X	X	X	X	X	X	X	X	X

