Yesterday, was the headache made worse by your usual daily activity	Yes	Migraine Criteria A
	No	
Q4. Yesterday, did the headache come with sensitivity to light and sound?	Yes	Migraine Criteria B
	No	
Q5. Yesterday, did you feel sick to the stomach or throw-up with the headache?	Yes	Migraine Criteria B
	No	
Q6. Yesterday, did you take any medicine for your headache?	Yes	Medication will only count as headache medication on a day a headache occurred.
	No	
Q7. Do you believe you experienced a migraine AND it was relieved by a triptan or ergot derivative?	Yes	Migraine Criteria C
	No	

Abbreviation: Q = question.

^a If “No” is answered for Q1, then the patients will skip the other questions.

Efficacy Measure: the Number of Monthly Migraine Headache Days

One of the efficacy measures is the number of monthly migraine headache days. A migraine headache day is defined as a calendar day on which a **migraine or probable migraine** occurs.

The number of monthly migraine headache days will be summarized from the daily diary data for each patient in that period (including 30 days of daily data from the baseline period prior to randomization, 12 months of daily data during the treatment phase, and 4 months of daily data during the post-treatment phase).

The daily data will be aggregated, and the number of migraine headache days will be provided for each of the 30-day periods. In calculating the number of migraine headache days for each period, if the period is not equal to 30 days, the number of migraine headache days will be

normalized by multiplying the number of migraine headache days by $(30/x)$ where “x” is the total number of non-missing diary days in the period.

For SP III, Month 1 period data is based on headache information from Visit 3 up to on Visit 5-1 day. Month 2 period data is based on headache information from Visit 5 up to Visit 6 – 1 day. Month 3, to Month 12 will be defined similarly.

For the 4 months of the post-treatment period, the monthly interval will be derived as below. Firstly, the 2-month visit interval (60 days) will be split into two 1-month periods for efficacy measures. Day 1 (the first day of post-treatment period) to Day 30 will be for the first 1-month period and Day 31 to Day 60 for the second 1-month period. Even if diary is recorded longer than 60 days, these will be ignored.

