For patients who discontinued early during the post-treatment phase, if the date of discontinuation is within 30 days of previous visit date, all data between the previous visit date and the discontinuation date will go to 1 monthly period; if the date of discontinuation is more than 30 days of the previous visit date, then the first 30 days will be the first monthly period, and the rest will be considered as part of the second monthly period (up to 60 days).

Example 1: A patient has 64 days between Visit 17 and Visit 18. He completes the study on Visit 18. Then he has:

- 1st half month = diary data from Day 1 to Day 30
- 2nd half month = diary data from Day 31 to Day 60

Example 2: A patient has 44 days between Visit 17 and Visit 18. He discontinues the study on Visit 18 (i.e., disposition is not marked as completed). Then he has:

- 1st half month = diary data from Day 1 to Day 30
- 2nd half month = diary data from Day 31 to Day 44

Additionally, if the compliance rate for each monthly interval is $\leq 50\%$, then all endpoints to be derived from the diary data for that 1-month period will be considered missing. For the post-treatment phase, the derived 1-month periods (resulting from splitting 2-month visit interval) will be treated similarly.

For a patient who discontinued early in the treatment phase, the compliance rate for the last month of that study period will be calculated with the denominator of the maximum of 30 and the total number of calendar days in that month, i.e., $\max(30, \text{the total number of calendar days in that month})$.

For a patient who discontinued early in the post-treatment phase, the compliance rate for the last month of that study period will be calculated with the denominator of 30. (For example, as shown above in Example 1, Visit 17 and Visit 18 can be split into 2 months. Each of them can

have 30 days as maximum duration.) For the rest of months and patients, the compliance rate will be calculated as described in Section 5.5.7.

The Other Efficacy Measures

The same approach to adjusting the number of days within each period to a 30-day period and the same approach to imputing monthly data based on compliance as described above will be applied to all efficacy measures that are derived from diary data and need normalization to 30-day period, including:

- **Number of headache days** is calculated as the number of calendar days in a 30-day period on which a headache occurs.

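### The fixed 30-day denominator for follow-up diary compliance marks down complete diaries in Months 14 and 16 when the follow-up visit is early but in window

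*SAP*

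**What the plan says.** SAP 5.5.7 gives two denominators for diary compliance. In general the expected number of days "is based on actual visit date for that particular period (Month"; its worked example takes Month 3 as the date of Visit 7 minus the date of Visit 6. For follow-up it says: "Expected number of Diary days for Month 13, Month 14, Month 15, and Month 16 in SP IV is 30 days". There is one exception on the treatment side. For a patient who leaves early in Study Period III, "the last month compliance is based on max (30, the total number of calendar days in that month").

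SAP 5.4.1 decides who gets which rule. It sets 30 as the denominator for one group: "For a patient who discontinued early in the post-treatment phase, the compliance rate for the last month of that study period will be calculated". Then: "For the rest of months and patients, the compliance rate will be calculated as described in Section 5.5.7". Patients who did not discontinue are therefore sent to 5.5.7, where the follow-up figure is again 30.

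SAP 5.4.1 also splits each two-month follow-up interval in two, the later span being the second month: "Day 1 (the first day of post-treatment period) to Day 30 will be for the first 1-month period and Day 31 to Day 60". Extra days do not count: "Even if diary is recorded longer than 60 days, these will be ignored". If a month's compliance is 50% or less, all its diary endpoints are missing. Otherwise its counts are scaled by 30/x, where x is the number of non-missing diary days.

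In the Schedule of Activities of the protocol addendum for CM patients, Visits 17 and 18 have a target interval of 60 days, and the row "Interval allowance (days) compared from previous visit" gives ±7 for both.

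**The concern.** A compliance percentage should measure how much of the diary a patient filled in out of the days on which it could be filled in. With a fixed 30, a patient who attends a few days early, within the permitted window, is marked down for days that never existed. A late visit gives no offset, since days after Day 60 are dropped. Months 13 and 15 are unaffected within the window because they always hold 30 days, so the shortfall falls only on Months 14 and 16.

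Two outputs are touched. The first is the compliance report in 5.5.7: the monthly figures, the overall follow-up average, and the counts of patients at or above 80% and 50%. The second is the rule for missing months, which uses the same percentage. In CM patients a month lost in follow-up drops out of the combined Study Period III/IV repeated-measures analysis of migraine headache days. In all arms it drops out of the descriptive diary summaries. Month-by-month response status, on which time to loss of 50% response depends, is also derived from these data. These results serve the secondary objective on residual effect after treatment.

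**Working it through.** Inputs:
- Follow-up interval L: 60 ± 7 days, so 53 to 67 (protocol addendum, Schedule of Activities, CM patients; the episodic migraine (EM) schedule is not in the supplied text).
- Split at Day 30, with days after 60 ignored (SAP 5.4.1).
- Denominator 30 in follow-up, actual days in an ordinary treatment month (SAP 5.5.7).
- Month missing if compliance is ≤ 50% (SAP 5.4.1).

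**Check against the plan's own examples.** First month = min(L, 30) and second month d = min(L, 60) − 30. For L = 64 this gives 30 + 30 days, and for L = 44 it gives 30 + 14 days. Both match the examples in SAP 5.4.1, which state no compliance percentages.

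**Complete diary in the second month.** Score = d/30 under the follow-up rule and d/d = 100% under the ordinary treatment-month rule.

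**Missing status.** With e entries, the follow-up rule discards the month if e/30 ≤ 0.5, that is e ≤ 15. The treatment-month rule discards it if e/d ≤ 0.5. The two disagree when d/2 < e ≤ 15.

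| L (days) | d (days) | Complete diary, d/30 | Entries discarded in follow-up but kept under the treatment rule | As % of available days |
|---|---|---|---|---|
| 53 | 23 | 76.7% | 12–15 | 52.2–65.2% |
| 54 | 24 | 80.0% | 13–15 | 54.2–62.5% |
| 55 | 25 | 83.3% | 13–15 | 52.0–60.0% |
| 56 | 26 | 86.7% | 14–15 | 53.8–57.7% |
| 57 | 27 | 90.0% | 14–15 | 51.9–55.6% |
| 58 | 28 | 93.3% | 15 | 53.6% |
| 59 | 29 | 96.7% | 15 | 51.7% |
| 60–67 | 30 | 100% | none | – |

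**Like for like.** Most treatment intervals are 30 ± 7 days, so a 23-day month is allowed there too. Fifteen entries in a 23-day treatment month score 15/23 = 65.2% and the month is kept. Fifteen entries in a 23-day Month 14 score 15/30 = 50.0% and the month is missing.

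**When would a complete diary be lost?** Only if d/30 ≤ 0.5, so d ≤ 15 and L ≤ 45 days, which is outside the window. The SAP's own 44-day discontinuer is such a case: 14/30 = 46.7%. A complete 14-day last treatment month of an early discontinuer gives the same figure, 14/max(30, 14) = 46.7%.

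**80% line.** Within the window only L = 53 takes a complete diary below 80%; L = 54 gives exactly 80.0%. Some part-filled diaries at 53 to 58 days also fall below it although at least 80% of the available days were filled.

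**Overall follow-up compliance.** With complete diaries and both intervals at 53 days, (100 + 76.7 + 100 + 76.7)/4 = 88.3%.

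**Average effect.** This depends on visit timing, which the documents do not give. For complete diaries the Month 14 or 16 mean lies between 76.7% (every interval 53 days) and 100% (every interval 60 days or more). If intervals were spread evenly over 53 to 67 days, which is only an assumption, 7 of 15 interval lengths would score below 100% and the mean would be 93.8%.

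**The case against.** The rule is explicit and has a logic. SAP 5.4.1 defines a month as 30 days, and the eCRF collects follow-up counts in fixed blocks for Days 1–30 and 31–60, so 30 matches the block. In treatment the month is the visit interval, so visit dates are the natural denominator. The fixed 30 also acts as a data floor: a follow-up month is kept only with at least 16 entries. Without it, a month with 12 entries would be kept and its counts multiplied by 30/12 = 2.5. The floor is a defensible choice, and relaxing it has a small cost. Follow-up is not stricter in every comparison either: a 37-day treatment month needs 19 entries to be kept. What the objection does not justify is reporting the floor as a compliance percentage, since a complete diary is then shown as incomplete.

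A reader might infer several stronger points that the documents do not support:

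- That a 77% score causes data loss. The cut-off is ≤ 50%, so every complete in-window month is kept.
- That treatment months always use actual days. An early discontinuer's last treatment month uses the larger of 30 and the calendar days, so a 30-day minimum denominator exists in both periods.
- That the planned ANOVA would test the drop at Months 14 and 16. It compares treatments within a month, and the arms share the same visit schedule and denominator. Nothing in the documents points to a difference between arms from this source.
- That many patients are affected. A loss needs both an early visit and a part-filled diary. CM patients had to complete at least 80% of diary entries at baseline (inclusion criterion 7), which does not guarantee later compliance but gives no reason to expect many at 52% to 65%.

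**Conclusion.** The point stands as a minor one. For patients who remain in follow-up and attend 53 to 59 days after the previous visit, the compliance figure for Month 14 or 16 is too low by construction. The shortfall for a complete diary is 23.3 percentage points at 53 days, falling to 3.3 at 59 and zero from 60 days. For part-filled short months, the effective cut-off for missing data rises from 50% of available days to at most 65.2%. Both results follow directly from the stated rules. The number of patients affected cannot be computed from the documents. The ±7-day window is confirmed only for CM patients (about 60 of about 300 planned), and applying it to EM patients would be an assumption. The primary safety objective is not touched.

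**What to change.** In SAP 5.5.7, for patients who did not discontinue during the follow-up interval, define expected diary days for the second month (Months 14 and 16) as min(30, days from Day 31 to the day before the visit). Keep 30 for patients who discontinue in that interval. A complete in-window diary then scores 100% at every interval.

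Apply the same denominator to the ≤ 50% rule in SAP 5.4.1 so that follow-up and ordinary treatment months are handled alike. The price is that a few short months with 12 to 15 entries would be kept and scaled by between 30/12 = 2.5 and 30/15 = 2.0, as already happens for equally short treatment months. If a minimum of 16 entries is what the sponsor intends for follow-up, state it as a separate missing-data rule and leave it out of the compliance figure.

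Either version is about one line in the derivation. It needs no new data, since the eCRF already holds the diary days completed in Days 31–60 and the visit dates supply the rest.

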5.5.8. Previous Migraine Prevention Therapy and Previous Migraine Acute Treatment

For previous migraine prevention therapy summary, treatment group is based on (EM120, EM240, CM120, CM240)

The proportion of patients who received previous migraine prevention therapy, and the proportion of patients with response to the previous migraine prevention therapy within each of

the 6 categories (to enter this trial, medical history event, adequate response, inadequate response, no response, and treatment availability) will be summarized for ITT patients. (Those reasons are captured at EM: CGAN Visit 1, CM: CGAP Visit 1). Treatment group comparisons will be done using the Fisher's exact test.

Previous migraine prevention therapies are migraine prevention therapies that started prior to the date of the first injection and stopped prior to or at the date of first injection (CGAN Visit 3 for EM patients, CGAP Visit 3 for CM patients) which has indication recorded in the CRF (prior therapy migraine medication, or concomitant medication) as one of the followings:

- [1] "Primary study condition" (except acute treatment)
- [2] Corresponding medical history event (preferred term) that includes "migraine" (except acute treatment)
- [3] Corresponding adverse event (preferred term) that includes "migraine" (except acute treatment)

Note that all records in the prior therapy migraine medication CRF have the indication "primary study condition".

Previous migraine prevention therapy and migraine prevention therapy during SP III and SP IV (Section 5.5.9) will be reviewed by medical to exclude non-migraine prevention therapy before DBL.

Previous migraine acute treatment during baseline (EM: CGAN Month 6, CM: SP II) will be summarized by following categories (can be multiple classes):

- triptans,
- NSAIDs/aspirin,
- acetaminophen/paracetamol,
- ergots,
- anti-nausea
- Chinese medicine
- Others

Previous migraine acute treatment are migraine acute treatment used in during the baseline. Migraine acute treatments will be identified by the concomitant medication CRF with one of the following indications:

- [1] "Primary study condition" (except migraine prevention therapies)
- [2] Corresponding medical history event (preferred term) that includes "migraine" (except migraine prevention therapies)
- [3] Corresponding adverse event (preferred term) that includes "migraine" (except migraine prevention therapies)

Previous migraine acute treatment and migraine acute treatment during SP III and SP IV (Section 5.5.9) will be reviewed by medical to exclude non-acute treatment and to categorize them into the above definitions before DBL.

Regarding migraine acute treatment (and previous migraine acute treatment), combination medications (such as aspirin/acetaminophen/caffeine) will be counted in each medication category that applies (such as NSAIDs/aspirin and Acetaminophen/paracetamol).

